**Principal Investigator: [name].**

**Desmopressin as a therapy for nocturnal enuresis in patients with Sickle Cell Disease**

**January 20, 2020**

**Background:**

Nocturnal enuresis is more prevalent in patients with sickle cell disease (SCD) than the general pediatric population. The International Children’s Continence Society (ICCS) defines enuresis as discrete episodes of urinary incontinence during sleep in children  $\geq 5$  years of age. The rate of nocturnal enuresis in patients with sickle cell disease (Hemoglobin SS, SB0thal and SB+thal) ranges from 28% to 52% of boys and 11% -38% of girls, compared to 7% of boys and 3% of girls at age 5 in the general population. Enuresis becomes less common with age, in one study decreasing from 36% in patients between 8-10 years to 9% of patients aged 18-20 years. Nocturnal enuresis has been shown to affect patient’s quality of life, and can lead to social and emotional stigma, stress and inconvenience. Currently, there is no mainstay of therapy for nocturnal enuresis in patients with SCD. In the general pediatric population, several therapies are used to manage nocturnal enuresis, including behavior modification, alarms and pharmacotherapy such as desmopressin and less often, imipramine. Desmopressin is a synthetic analogue of arginine vasopressin which exerts an antidiuretic effect by increasing water reabsorption in the distal tubules and collecting ducts of the kidneys. In the general pediatric population, bed-wetting was reduced by 1.34 nights per week (95% CI 1.11-1.57) in patients who received desmopressin compared to those who received placebo. Patients receiving desmopressin were almost twice as likely to achieve at least 14 consecutive dry nights compared to placebo.

Desmopressin is not systematically prescribed to patients with SCD who have nocturnal enuresis. This may be due to the thought that these patients have an irreversible and progressive defect in the renal medulla secondary to chronic sickling episodes, and desmopressin may be ineffective, as this defect is not related to the signaling pathways in which desmopressin acts. This also may be due to lack of adequately powered clinical trials demonstrating efficacy. More likely, patients with SCD have many medical complications associated with their disease and symptoms of seemingly lesser conditions such as nocturnal enuresis may be minimized or ignored.

---

 Nevés, T., et al., *The standardization of terminology of lower urinary tract function in children and adolescents: report from the Standardization Committee of the International Children's Continence Society*. The Journal of Urology, 2006. **176**(1): 314-324.

 Barakat, LP., et al., *Nocturnal Enuresis in Pediatric Sickle Cell Disease*. Journal of Developmental and Behavioral Pediatrics, 2001. **22**(5): p. 300-305

 Readett, D R J., et al., *Nocturnal enuresis in sickle cell haemoglobinopathies*. Archives of Disease in Childhood, 1990. **65**: 290-293

 DeBaun, M R., et al., *Enuresis Is a Common and Persistent Problem Among Children and Young Adults with Sickle Cell Anemia*. Urology, 2008. **72**(1):81-84

 Naitoh, Y., et al., *Health Related Quality of Life for Monosymptomatic Enuretic Patients and Their Mothers*. The Journal of Urology, 2012. **188**(5): 1910-1914

The mechanism underlying the higher prevalence of enuresis in patients with sickle cell disease is not completely understood. Several hypotheses have been studied and the etiology is thought to be multifactorial. The predominant theory proposes that enuresis occurs secondary to a defect in the concentrating capability of the kidney caused by the sickling of red blood cells in the hypertonic, acidic and hypoxic renal medulla. Sickling leads to occlusion of the vasa recta and impairment of blood flow. This interferes with the countercurrent mechanism of the kidney, and impedes free water reabsorption leading to increased urinary volume, hyposthenuria and oftentimes delayed attainment of nocturnal urinary continence.

Several studies support this theory by demonstrating decreased urine osmolality in patients with sickle cell disease compared to healthy controls. Stadius Van Eps et al, demonstrated that patients with Hemoglobin SS disease have decreased urine osmolality at a young age compared to patients with Hemoglobin SC, AS and AA, with a progressive decline over time until a plateau at approximately age ten. Noll et al compared patients with sickle cell disease to sibling controls to demonstrate higher rates of enuresis and nocturia in patients with SCD correlating with decreased urine specific gravity measurements. Readett et al challenged this hypothesis by comparing urine osmolality of enuretic patients with SCD to non-enuretic patients with SCD, demonstrating no significant difference in the urine osmolality after a water deprivation test between the two groups. Their study showed that enuretic patients had a lower maximum functional bladder capacity and higher overnight urine volume to bladder capacity ratio compared to controls, suggesting that these factors may contribute to enuresis in patients with sickle cell disease. The study also collected subjective data from families who assessed patients with nocturnal enuresis as deep sleepers. In another study, Readett et al noted a correlation between large family size and likelihood of enuresis in boys, further suggesting a social and environmental component to enuresis.

Few studies have been done to evaluate the efficacy of standard therapies for nocturnal enuresis in patients with SCD. One study by Figueroa et al supports the use of desmopressin in patients with SCD. This study examined a population of 91 patients with sickle cell disease age 6-21 with a 29.6% prevalence of nocturnal enuresis. The researchers looked at the effect of enuresis alarms and intranasal desmopressin on the rate of nocturnal enuresis. Ten patients elected to receive desmopressin, with four showing complete resolution of symptoms, and two showing greater than 50% improvement of symptoms while receiving medication, an overall 60% rate of improvement. Two patients elected to use enuresis alarms with no improvement in symptoms after three and four months respectively. While this study showed the desmopressin may be effective in this population, it was limited by its small sample size and lack of randomization or blinding. This study also used intranasal desmopressin, which is not routinely

---

 Becker, A, *Sickle cell nephropathy : challenging the conventional wisdom*, Pediatric Nephrology, 2011. **26**: 2099-2109

 Stadius Van Eps, LW., et al., *The relation between age and renal concentrating capacity in sickle cell disease and hemoglobin C disease*. Clinica Chimia Acta, 1970. **27**: 501-511

 Noll, JB., et al., *Enuresis and Nocturia in Sickle Cell Disease*. The Journal of Pediatrics, 1967. **70**: 965-967

 Readett, D R J., et al., *Determinants of Nocturnal Enuresis in Homozygous Sickle Cell Disease*. Archives of Disease in Childhood, 1990. **65**:615-618

 Figueroa, E., et al., *Enuresis in Sickle cell Disease*. The Journal of Urology, 1995. **153**: 1987-1989

used as it is associated with variable absorption patterns and thus increased side effects compared to the oral preparation, including the serious side effect of hyponatremia.

A survey conducted from July to September 2010 at the CHAM Hematology clinic, where we follow over 600 sickle cell patients, showed that of 63 patients between the ages of 5-21, 27% reported nocturnal enuresis. Table 1 shows rates of nocturnal enuresis by age group in this population. This data is consistent with the increased rate of nocturnal enuresis previously reported, suggesting that we will have a more than an adequate number of patients eligible to participate in this study.

**Table 1**

Age	Enuretic	Non Enuretic	% Enuretic
5-10	8	28	22.2%
11-21	9	18	33.3%
Total	17	46	27 %

Our initial objective was to conduct a randomized placebo controlled double blinded study to assess the efficacy of desmopressin on the rate of nocturnal enuresis in patients with SCD compared to placebo. We also planned to utilize quality of life and fatigue scale questionnaires to evaluate the quality of life in these patients prior to and after treatment. We hypothesized that patients receiving desmopressin would demonstrate fewer episodes of nocturnal enuresis compared to those receiving placebo. Due to low accrual with the study (five participants completed the study and nine participants withdrew from the study), and due to the fact that DDAVP treatment for nocturnal enuresis is already standard of care in a general pediatric population, it was determined beneficial by the investigators to prescribe DDAVP as standard of care and to eliminate the placebo group. The study team will prospectively collect quality of life data for the patients prior to prescribing DDAVP and then one month after initiating treatment with DDAVP. Prior to starting DDAVP an eligibility diary would be filled out on recollection by patient on their enuresis patterns for the past 2 weeks (Appendix 1A). Enuresis diaries would be given to patients and families to track their enuresis but also could be filled out retrospectively with study coordinator either in person or over the phone. We propose to then analyze their laboratory, physical exam, imaging, data prospectively for those patients administered DDAVP as part of their clinical care upon starting the DDAVP. We would prospectively administer surveys on willing participants prior to starting DDAVP and then one month into the intervention. To provide information to the sickle cell research community we propose the following interventions.

The primary objective of this study is:

1. To prospectively assess if the use of desmopressin in patients with sickle cell disease and nocturnal enuresis will decrease the number of nighttime episodes of enuresis by 50% after initiating DDAVP at 0.4 mg nightly dose with dose escalation as clinically appropriate.

Secondary objectives are:

1. To determine if patients with sickle cell disease and nocturnal enuresis receiving desmopressin will have an improved quality of life compared to their baseline.
2. To determine if patients with sickle cell disease and nocturnal enuresis receiving desmopressin will have less daytime fatigue compared to their baseline data.
3. To determine if the use of desmopressin in patients with nocturnal enuresis improves rates of nocturia, defined as episodes of nighttime awakening to void in children  $\geq 5$  years of age, compared to prior to initiating treatment with DDAVP.

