### **Population:**

#### Inclusion Criteria:

1. Patients with Hemoglobin SS, SC, SB0thal or SB+thal
2. Patients age 8-21
3. Patients with at least two episodes of primary nocturnal enuresis per week or four episodes over the two weeks prior to enrollment.
4. Patients with secondary enuresis who have been evaluated and cleared by a pediatric urologist as not having other etiologies of enuresis (e.g. overactive detrusor activity, a genitourinary anatomic abnormality)

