### **Enrollment:**

This study will be a cohort analysis of a standard of care medication administered for nocturnal enuresis. Prior to starting this standard of care medication patients will fill out the PROMIS questionnaire on fatigue. Patients with sickle cell disease who fit the inclusion criteria will be notified about the study when they are seen in hematology clinic, prior to discharge from hospitalization or via phone by study staff. Patients enrolled during hospitalization will not start the trial until a post-hospitalization follow up visit. At this point, the study will be introduced and discussed. Written consent for the survey will be obtained from interested and eligible guardians, or patients, if they are older than 18 years old or an emancipated minor. Patients 7-17 years of age will sign assent. Patients will also be identified for eligibility via the electronic medical record. Patients who fit the inclusion criteria will be called and informed of the medication following a detailed script (see Appendix 6). If they are interested, consent will be obtained at the next outpatient or inpatient visit. Patients and/or guardians will have the option to decline participation or opt out of the study at any point.

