### **Monitoring**

Patients will be asked to keep an “enuresis diary” for four weeks (See Appendix 1B). In the diary, patients will record their adherence to the medication, if they had an episode of enuresis, as well as the number of nighttime awakenings specifically secondary to nocturia (and not for

any other reason such as pain or anxiety). All patients will have a follow up call two weeks and four weeks after starting the medication by the study coordinator. Patients will be assessed for improvement in symptoms, medication adherence, and any side effects they are experiencing. Blood pressure, Chem-10, Urine and serum electrolytes and osmolality and urine analysis will be obtained if patient describes any adverse clinical symptoms as would be performed as part of standard of care. Enuresis diaries will be reviewed, and if patients do not have at least a 50% improvement in symptoms they will be advised to make an appointment to investigate if adjustment of the medication based on clinical care would be appropriate. See Appendix 3 for a complete study timeline.

Any patient that has a dose dependent side effect to the medication will have the dose reduced promptly and appropriate clinical management and follow up. If a patient has an acute VOC while taking study medication and is on intravenous fluids, the medicine will be held during the acute event. Individuals will be asked at the end of the study if they had a pain crisis or acute chest syndrome during this intervention.

Be advised that the patients will have up to one year to complete the study. Although the study should only take 4 weeks the patient will not be removed from study unless their participation lasts longer than one year. Children with sickle cell disease frequently have admissions related to their chronic disease that may prevent them from completing study within the 4 week time period. The medication works immediately and a stop in the medication will not cause a decrease in effect of the previous or current doses.

Study tools:

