Promis Fatigue scale- PROMIS® instruments use modern measurement theory to assess patient-reported health status for physical, mental, and social well-being to reliably and validly measure patient-reported outcomes (PROs) for clinical research and practice. PROMIS instruments measure concepts such as pain, fatigue, physical function, depression, anxiety and social function. The Fatigue scale utilizes a 7-day recall period (items include the phrase "the past 7 days") with five responses. The responses span from never (0) to almost always (4). The Fatigue scale is a 10 item questionnaire whose scores can be approximated if a participant skips a question. A 10-item short form can be scored as long as the participant answered at least 5 items. The Pediatric PROMIS Fatigue scale has been validated for patients aged 8-17 years of age. The surveys will be administered at initiation of medication (week 1) and after completion of 4 weeks of medication. If patients stop and restart the medication the survey will be taken after 4 consecutive weeks of at least 50 % compliance with the medication. This will assess differences in the patients' perception of fatigue after starting the medication. Please see Appendix 4 for Promis Fatigue Scale.

Statistics:

For our study, success in treatment will be defined as a 50% reduction in bedwetting episodes. Our primary endpoint is the improvement in number of wet nights (binary outcome variable) comparing pretreatment and post treatment use of desmopressin. We can expect little or no change in untreated subjects and therefore presume that maximum 10% will improve on their own. Based on the study by Figueroa et al, we can presume that 60% of patients will improve

with desmopressin treatment. In order to detect this 50% difference, we will enroll 50 patients for the study so that the 95% CI for proportion of subjects with improvement after treatment is expected to be (0.46, 0.74) thus will be able to exclude 10% that is expected for untreated subjects. In a secondary analysis, the improvement status will also be correlated to patient characteristics using a logistic regression model. Secondary endpoints are not powered

 Magasi, S. et al. (2011). Content validity of patient reported outcomes: Perspectives from a PROMIS meeting. Quality of Life Research, 25 Aug 2011.

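### The 50% endpoint is tied to no baseline count or follow-up window; if the recalled entry fortnight is the denominator, regression to the mean may produce more no-drug responders than the presumed 10%

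*Combined protocol and SAP*

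**What the plan says.** All references are to the combined protocol and SAP.

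- **Endpoint (Statistics).** Success is a halving of bedwetting episodes, analysed as a binary outcome "comparing pretreatment and post treatment use of desmopressin". Neither side of the comparison is given a window. The primary objective (Background) says only that the fall occurs after DDAVP is started.
- **Pretreatment count (Background, after Table 1).** "Prior to starting DDAVP an eligibility diary would be filled out on recollection by patient on their enuresis patterns for the past 2 weeks". The Intervention section also speaks of baseline data from the preceding six months, but names history and laboratory items there and no wet-night count.
- **Entry (Inclusion Criteria).** Criterion 3 admits "Patients with at least two episodes of primary nocturnal enuresis per week or four episodes over the two weeks prior to enrollment". Criterion 4 admits "Patients with secondary enuresis who have been evaluated and cleared by a pediatric urologist" and states no frequency.
- **Timing (Enrollment).** "Patients enrolled during hospitalization will not start the trial until a post-hospitalization follow up visit", so the fortnight before enrollment and the fortnight before DDAVP can differ.
- **Follow-up (Monitoring).** A diary is kept for four weeks, and "All patients will have a follow up call two weeks and four weeks after starting the medication by the study coordinator". Patients have up to one year to finish. None of these is named as the endpoint window, and no rule puts a two-week and a four-week count on one scale.
- **Comparator (Statistics).** The plan will "presume that maximum 10% will improve on their own", without a source. It expects 60% on treatment, and concludes from the 95% interval excluding 10%. The placebo group has been removed.

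**The concern.** A patient whose wet nights vary by chance is more likely to enter after a bad fortnight than after a good one. If that same fortnight is then the denominator, the next four weeks will tend to look better even if the drug does nothing. Some patients will cross the 50% line for this reason alone.

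A concurrent control would show how many. Here the only protection is the presumed 10% maximum, and the plan does not say whether that figure allows for selection on the baseline count. If the true no-drug rate under the chosen definition is higher, a modest response could exclude 10% and be reported as a drug effect. The size of the estimated benefit would also be inflated.

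Leaving the windows open adds a second problem: the follow-up period could be settled after the data are seen.

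**Working it through.** **1. The plan's own interval.** With n = 50 and p = 0.60, the Wald interval is 0.60 ± 1.96 × √(0.60 × 0.40 / 50) = 0.60 ± 0.136, or (0.464, 0.736). This rounds to the stated (0.46, 0.74).

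**2. What it takes to exclude a given rate.** The Wald lower limit is p − 1.96 × √(p(1 − p)/50).

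| Responders of 50 | Lower limit |
|---|---|
| 10 | 0.089 |
| 11 | 0.105 |
| 16 | 0.191 |
| 20 | 0.264 |
| 21 | 0.283 |
| 22 | 0.302 |
| 30 | 0.464 |

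So 10% is excluded from 11/50 (from 10/50 with a Wilson or Clopper-Pearson interval), 18.5% from 16/50, 26% from 20/50 and 30% from 22/50.

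**3. No-drug response when the entry count is reused.** Let B be wet nights in the 14-night entry fortnight and F wet nights in 28 follow-up nights. Response means F/28 ≤ 0.5 × B/14, which reduces to F ≤ B. The quantity needed is P(F ≤ B | B ≥ 4) with the same nightly risk in both periods.

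For illustration, take a patient with true risk 0.20. The chance of entry, P(B ≥ 4), is 0.30. If that patient enters with B = 4, the chance of counting as a responder with no drug effect is P(F ≤ 4 of 28) = 0.31. At true risk 0.30 the latter falls to 0.05. The problem sits near the entry cut-off.

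For a population, the assumptions are independent nights, constant individual risk, accurate recall, everyone entering at 4 or more of 14, and nightly risk following a beta(a, b) distribution. A larger a + b means patients are more alike.

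| Mean nightly risk | 0.15 | 0.2 | 0.3 | 0.4 | 0.5 | 0.6 |
|---|---|---|---|---|---|---|
| Entry count reused, a+b = 4 | 18.5% | 15.9% | 11.3% | 7.6% | 4.8% | 2.8% |
| Separate 14-night baseline, a+b = 4 | 9.4% | 8.4% | 6.4% | 4.6% | 3.2% | 2.0% |

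Over means 0.15 to 0.4, the reused count gives 12.8% down to 6.7% at a+b = 2, and 26.0% down to 7.9% at a+b = 8.

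**4. Departures from those assumptions.**

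- Drift between fortnights: with logit-normal risk (mean −1.8, SD 1.2), the no-drug rate is 18% with stable rates and 27% with an added fortnight-to-fortnight SD of 0.5 on the logit scale. Over a wider set of logit-normal cases (median risk 0.2 to 0.4, drift SD 0.5 to 1.0) it is 11% to 37%.
- Recall: an assumed 25% error moves the reused-count rate to 4–11% if wet nights are under-recalled and 14–28% if over-recalled.

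**5. Chance of excluding 10% with no drug effect.** This is P(X ≥ 11 | 50, r).

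| True no-drug rate r | 10% | 7.6% | 11.3% | 15.9% | 18.5% |
|---|---|---|---|---|---|
| P(X ≥ 11) | 0.9% | 0.1% | 2.2% | 16% | 31% |

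**6. The planned result.** At r = 18.5%, the chance of 23/50 or more is about 0.00001. At 30/50 the lower limit of 0.464 lies above every rate in steps 3 and 4.

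**The case against.** The strongest reply is that the harm needs three things together: the recalled fortnight must be the denominator, many patients must sit near the cut-off, and the observed response must fall well below plan. All three points stand.

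- **Reuse is not established.** Appendices 1A, 1B and 3 are cited but not supplied, and may hold part of the definition. Criterion 4 gives no frequency, and the two fortnights can differ for patients enrolled in hospital. A reader might infer that the plan does divide by its own entry count; the text makes this likely but does not say it.
- **The 18.5% uses the lowest mean shown**, where about 51% of entrants have only 4 or 5 wet nights. With stable rates and mean risk of 0.4 or more, 10% covers the effect.
- **The planned conclusion is safe.** If the true response is 60%, the chance of 15/50 or fewer is about 0.00002.
- **A two-week endpoint window is only not ruled out.** It would give 23.7% to 11.6% at means 0.15 to 0.4 (a+b = 4). Since a four-week diary is described, these figures deserve little weight.

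What the reply does not remove is the decision rule. The 60% rests on 6 of 10 patients in an uncontrolled study of a different formulation, so a result well short of it is possible. In that range, excluding an unsourced 10% cannot separate drug from selection.

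**Conclusion.** The concern holds conditionally and should be fixed. In the supplied text the endpoint has no stated baseline or follow-up window. If the recalled entry fortnight is the denominator, the no-drug response is about 3% to 26% under the stable beta models shown, below 10% at mean nightly risk of 0.4 or more, and higher with drift between fortnights (18% rising to 27% in one assumed case). Results of 11 to 19 of 50 exclude 10% but not 26%; 20 of 50 still does not exclude 27%. That is the exposed band.

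All these rates are assumptions, because the documents give no distribution of wet nights.

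Two stronger readings are not supported. A reader might infer that a 60% response could be a selection artefact, or that 50 patients is too few; steps 1 and 6 show neither. A reader might also infer that 10% is simply too low; with frequent, stable wetting it is adequate.

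**What to change.** In the Statistics section:

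1. **Define response.** Wet nights per recorded night over the full four-week diary are at most half the per-night rate in the recalled fortnight.
2. **Change the inference.** Do not conclude a drug effect from excluding 10% alone. Describe the result as a before-after response, compare the 95% lower limit with a prespecified range of no-drug rates (for example 10% to 30%, stated as an assumption), and report the largest no-drug rate that the data exclude. As guides, 16/50 is needed to exclude 18.5%, and 20/50 to exclude 26%.
3. **Optional, exploratory.** Report a selection-adjusted model: a beta-binomial truncated at the entry threshold, a two-class alternative, and a range for recall error. State its constant-rate assumption. It should not be a success gate. When nightly risks of 0.2 or 0.7 (70:30) were simulated with no drug effect, requiring the beta-binomial adjustment as well cut false claims only from 26% to 23%. One count per patient also cannot separate drift from differences between patients.

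A separate pretreatment diary is not requested. It lowers the no-drug response but does not remove it (up to 12.6% at a+b = 8), and it adds burden where five participants completed and nine withdrew.

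Items 1 and 2 cost a few sentences and need no new visits, forms or patients; item 3 adds analysis time. The downside is a less favourable comparator and a weaker claim if the observed response is modest.

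### Secondary objective 3 needs a nocturia rate before DDAVP, but the protocol body describes awakenings to void as recorded only in the on-treatment diary

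*Combined protocol and SAP*

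**What the plan says.** The third secondary objective (end of the Background section) is to find out whether desmopressin "improves rates of nocturia, defined as episodes of nighttime awakening to void in children" aged 5 or over, "compared to prior to initiating treatment with DDAVP". That is a before-after comparison within patients.

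Two diaries are described:

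- **Before treatment** (Background, redesign paragraph, form in Appendix 1A): an "eligibility diary would be filled out on recollection by patient on their enuresis patterns for the past 2 weeks".
- **After starting** (Monitoring, form in Appendix 1B): a four-week diary. "In the diary, patients will record their adherence to the medication, if they had an episode of enuresis", and also "the number of nighttime awakenings specifically secondary to nocturia", leaving out awakenings for reasons such as pain or anxiety.

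The Intervention section adds the other baseline material: SCD-specific and general medical history (Appendix 2A), baseline data and laboratory results from the preceding 6 months (Appendices 2B to 2D), a renal sonogram unless a normal one is already on file, and the PROMIS Fatigue scale on the day DDAVP starts. The Statistics section defines no nocturia endpoint, baseline window or analysis, and states that secondary endpoints are not powered.

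**The concern.** A before-after objective needs the same quantity measured on both sides of the first dose. The body text describes nocturia on one side only. If data collection follows that text and the forms add nothing to it, the study will finish with an on-treatment rate of awakenings and nothing to set it against.

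In a controlled trial a missing baseline costs precision. Here the placebo group has been eliminated, so each patient's own pre-treatment value is the only comparator. The loss is also hard to repair: a baseline asked for at the end would be recalled after treatment by patients who know they were treated.

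An on-treatment rate is also hard to read alone. On the protocol's own definitions, enuresis happens during sleep and nocturia on waking. A night that used to be wet could become a night with an awakening, so even the direction of change cannot be assumed. That last step is inference from the definitions, not a result in the documents.

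**Working it through.** **The plan's own figure.** The only design figure is the confidence interval for the primary endpoint. With p = 0.60 and n = 50, the Wald interval is 0.60 ± 1.96 × √(0.60 × 0.40 / 50) = 0.60 ± 1.96 × 0.0693 = 0.60 ± 0.136, or (0.464, 0.736). This rounds to the stated (0.46, 0.74). It concerns bedwetting response and does not depend on nocturia.

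**Nocturia.** The documents give no baseline rate, standard deviation, effect size or test, so nothing can be computed. The check is a trace of where the variable is collected.

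| Source | Timing | Described content | Awakenings to void named? |
|---|---|---|---|
| Eligibility diary, Appendix 1A | Before first dose, 2-week recall | Enuresis patterns | No; form not seen |
| Medical history, Appendix 2A | Baseline | SCD-specific and general history | No; form not seen |
| Baseline data and labs, Appendices 2B to 2D | Prior 6 months | Not itemised beyond labs | No; forms not seen |
| Renal sonogram | Baseline | Degree of fibrosis | No |
| PROMIS Fatigue | Day of starting DDAVP, and after 4 weeks | Fatigue, 7-day recall | No |
| Four-week diary, Appendix 1B | On treatment | Adherence, enuresis, awakenings to void | **Yes** |

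The reasoning runs in four steps.

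1. The four-week diary is an on-treatment record, because adherence to the medication is one of its fields.
2. The eligibility diary has a purpose that does not require nocturia: the inclusion criterion counts enuresis episodes only (two per week, or four over two weeks).
3. Fatigue, the other before-after secondary outcome with an instrument, has a named scale and two stated time points. Nocturia has a careful on-treatment definition and no stated pre-treatment counterpart.
4. So no described source supplies the baseline. Whether an undescribed field does depends on Appendices 1A and 2A to 2D.

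**If the item is already on Appendix 1A,** the two measurements still differ. Baseline would be a recall of 2 × 7 = 14 nights. The on-treatment record covers 4 × 7 = 28 nights and, according to the redesign paragraph, may be kept by the family or filled in retrospectively with the coordinator. Totals are therefore not comparable; a rate per night is needed.

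**The case against.** The strongest reply is that this is an inference about forms that are not in the available text. The body gives the purpose of Appendix 1A in one line and does not list its fields. The label proves little, because the on-treatment form is also called an enuresis diary and does record awakenings to void. The Intervention section also has an open-ended baseline data item under Appendices 2B to 2D. This reply stands. It means the point has to be conditional, and that the first action is to look at the forms.

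Two stronger readings are therefore not supported. A reader might infer that no pre-treatment nocturia rate exists, so that objective 3 cannot be estimated at any sample size. The documents show only that none is described. A reader might also infer that comparing early with late diary weeks would miss most of the effect, because Monitoring says the drug acts at once. That remark is there to justify interruptions of treatment and gives no time course for nocturia. The dose may also change between early and late weeks. Such a comparison would not be the one the objective states, but no figure supports saying how much it would miss.

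It can also be said that the objective is secondary and unpowered. That limits the importance of the point but does not answer it: low power means an imprecise estimate, whereas a missing baseline means no estimate of the stated contrast.

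**Conclusion.** The concern holds in conditional form. As described in the body, the protocol collects nocturia only on treatment, while objective 3 requires a pre-treatment value. If none of Appendices 1A and 2A to 2D counts awakenings to void, all 50 planned patients will lack a baseline and the before-after comparison cannot be made; there is no control arm to fall back on. If one of them does, what remains is a smaller gap: the body still states no baseline window, summary measure or analysis for this objective, and the two records differ in length and in how they are completed.

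The conclusion assumes that the four-week diary starts with treatment, which its adherence field implies. The primary endpoint and sample size are not affected. The point should nevertheless be settled before further patients start, because a baseline not taken before the first dose cannot be reliably recovered.

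**What to change.** 1. Check Appendices 1A and 2A to 2D for a count of awakenings to void. If one is there, cite it in the body as the baseline for objective 3.
2. If not, add to the eligibility diary, completed before the first dose, the number of awakenings to void on each of the same 14 recalled nights. Use the restriction already given under Monitoring, so that awakenings for pain, anxiety or other reasons are not counted.
3. In Statistics, define the objective 3 endpoint as the within-patient change in awakenings per night: on-treatment awakenings divided by diary nights recorded, minus baseline awakenings divided by baseline nights recorded. Report the estimate with its confidence interval as unpowered.
4. State as a limitation that the baseline is recalled, while the on-treatment diary may be kept nightly or completed retrospectively, and record which was done for each patient.
5. For any patient who started without a baseline count, report on-treatment nocturia descriptively and make no before-after claim.

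The cost is at most one column on a form that is already filled in before treatment, plus a few lines in Statistics. The downside is that a recalled baseline is less precise than a nightly one.
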